9.2.9 WBC A₃AR Expression

At selected sites, a blood sample will be obtained at the Cycle 1 Day 1 (Baseline) visit, prior to dosing. 2.5 mL of blood are to be collected. The complete procedure is detailed in the laboratory manual provided by the central laboratory.

Sampling will be repeated at the beginning of every odd-numbered cycle, unless waived by the Sponsor.

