#### 5. CLINICAL PROCEDURES AND ASSESSMENTS

The schedule of clinical procedures and assessments conducted during the study is presented in the following table. Further details are given in the protocol.

TABLE 1–1: SCHEDULE OF EVENTS FOR DOUBLE BLIND (DB) PERIOD

			Cycle 1	Subse Cy	quent cles	End of Study/ End of Dosing (EOS) 	Follow-Up
Trial Procedures	Pre-Study (-28 days)	Day 1 Baseline	Days 8 and 15 ± 2 days	Day 1 ± 2 days	Day 15 ± 2 days	Day 1 + 2 days	(28 ± 3 Days Post- EOS)
Medical history	X						
Physical examination	X a	$X^{a,c}$	$X^{b}$	$X^{b}$	$X^{b}$	$X^{b}$	$X^{a}$
Inclusion/exclusion criteria	X	X					
Informed consent	X						
Body weight	X	X c		X		X	X
Vital signs d	X	X	X	X	X	X	X
Clinical laboratory testing e	X	X c	X	X	X	X	X
T3. T4, TSH	X	X		X		X	X
ECG f	X	X	X	X	X	X	X
Pregnancy test (serum) g	X	X c		X		X	X
ECOG PS g	X	X c		X		X	
α-fetoprotein (AFP)		X		X		X	X
WBC A3AR sample		X		$X^h$			
PK samples		$X^k$	$X^k$	$X^k$			
Hepatitis B/C virus serology	X						
Hepatitis B/C viral load (if		X		X i		X i	
seropositive)		Λ		Λ		Λ	
Tumor imaging for RECIST	$X^{j}$			$X^{j}$		X	
Concomitant medications	X	X	X	X	X	X	X
Adverse events		X	X	X	X	X	X
Dispense study drug supplies		X		X			
Review treatment compliance		X	X	X	X	X	

Symptom-directed examination.

c If Pre-Study assessment was performed \le 3 days prior to the Baseline Visit, assessments do not need to be repeated prior to

d Temperature, pulse, respiration, blood pressure at: Pre-Study; pre-dose at all visits; at 1, 2, 3, 4h (± 5 min), 6 and 8h (± 10 min) post-dose on Cycle 1 Day 1; and at Follow-up.

e See list of parameters in Appendix C.

FECG at Pre-Study; pre-dose at all visits; and at 2, 4, and 8h (± 10 min) post-dose on Cycle 1 Day 1; and at Follow-up.

Performed at Pre-Study, prior to the first dose, at the end of each cycle, and at Follow-up.

Day 1 of odd-numbered cycles, unless waived by the Sponsor (selected sites only).

For subjects with measurable viral load at the Baseline Visit; on Day 1 of odd-numbered cycles only and at EOS.

To subjects with heasthable vital load at the Baseline Visit, on Day 1 of odd-humbered cycles only and at EOS.

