#### 7.6.5 BIOMARKERS

The biomarker α-fetoprotein (AFP) will be assessed at Baseline, at Day 1 of each cycle, and at the follow-up visit. Summary statistics for AFP levels and CFB in AFP levels will be provided for the ITT Population by treatment and visit. Between-treatment comparisons will be performed by visit using Analysis of Covariance (ANCOVA) with CFB as the dependent variable and Baseline as the covariate. Summary statistics for AFP and CFB in AFP will be provided for each level of Overall Response for the ITT Population by treatment. Distribution of Overall Response will be presented for subjects with AFP levels <20, 20-200, or >200 ng/mL and for subjects with AFP levels above or at most the pooled median by treatment and cycle; the percentages will be calculated using number of subjects within each category defined by AFP levels as the denominator for each treatment.

WBC A3AR expression will be assessed at Baseline and at Day 1 of each odd-numbered cycle. Summary statistics for WBC A3AR expression and CFB in WBC A3AR expression will be provided for the ITT Population by treatment and visit. Summary statistics for CFB in WBC A3AR expression will be provided for each level of Overall Response for the ITT Population by treatment. To assess the relationship between Overall Response and changes in WBC A3AR at each visit, the distribution of Overall Response will be presented for subjects with WBC A3AR less than the pooled median and for subjects with WBC A3AR at least the pooled median at each post-baseline visit.

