#### 7.6.7 HEPATITIS VIRAL LOAD

Viral load for Hepatitis B Virus (HBV) and Hepatitis C Virus (HCV) for subjects with positive serology at Screening will be summarized using summary statistics for log-transformed values using the base 10 logarithm, which will be presented by treatment and visit for the ITT Population. Between-treatment comparisons will be performed by visit using ANCOVA with CFB for log-transformed values as the dependent variable and Baseline as the covariate. These variables (viral load (IU/mL) and log-transformed viral load) will be listed for the Safety Population. Any viral load recorded for subjects who do not have positive serology at Screening will not be included in tables but will be included in listings only.

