#### 8. MISSING DATA

Missing dates will be imputed only when the date is required to calculate the duration of an event for summary. As such, the only missing date that would need to be imputed is the date of final dose, required for calculation of duration of treatment. In such situations, the month and year would be recorded. For subjects who have completed dosing, the missing date of final dose will be imputed as the 15-th of the month; for subjects who are still receiving treatment, the missing date of final dose will be imputed as the date of the last completed visit.

Missing data from intermediate visits for AFP, WBC A3AR, viral load, and laboratory assessments when considered exploratory efficacy variables will be imputed using Last Observation Carried Forward (LOCF). Missing data for the latter laboratory variables will not be imputed when examined with laboratory assessments as safety variables. Due to the nature of the study, there is no imputation due to discontinuation.

The protocol specifies that certain assessments will not be repeated at Baseline (Cycle 1 Day 1) if assessed at the Pre-Study visit <= 3 days prior to Cycle 1 Day 1, resulting in missing values for Baseline; in such cases, the missing value at Baseline will be imputed by the value from the Pre-Study visit.

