CFB=Change from Baseline
Baseline=Cycle 1 Day 1
Missing data for intermediate visits are imputed using LOCF.

Source: Listing 16.2.6.4

Programming Note: Continue for all visits (Day 1 for each odd-numbered cycle through Cycle 11), including CFB.

Table 14.2.3.2 WBC A3AR expression at Baseline by Overall Response ITT Population

			CF102	Placebo
Visit	Overall Response	Statistic	(N=xx)	(N=xx)
Cycle 3 Day 1	CR	n	xx	XX
		Mean (SD)	xxx.x (xxx.xx)	xxx.x (xxx.xx)
		Median	XXX.X	XXX.X
		Min, Max	XXX, XXX	XXX, XXX
	PR	n	xx	XX
		Mean (SD)	xxx.x (xxx.xx)	xxx.x (xxx.xx)
		Median	xxx.x	XXX.X
		Min, Max	xxx, xxx	XXX, XXX
	SD	n	XX	XX
		Mean (SD)	xxx.x (xxx.xx)	xxx.x (xxx.xx)
		Median	xxx.x	XXX.X
		Min, Max	XXX, XXX	XXX, XXX
	PD	n	XX	XX
		Mean (SD)	xxx.x (xxx.xx)	xxx.x (xxx.xx)
		Median	xxx.x	XXX.X
		Min, Max	XXX, XXX	XXX, XXX
CFB at Cycle 3 Day 1	CR	n	XX	xx
,		Mean (SD)	xxx.x (xxx.xx)	xxx.x (xxx.xx)
		Median	xxx.x	XXX.X
		Min, Max	XXX, XXX	XXX, XXX
	PR	n	XX	XX
		Mean (SD)	xxx.x (xxx.xx)	xxx.x (xxx.xx)
		Median	xxx.x	xxx.x
		Min, Max	XXX, XXX	XXX, XXX
	SD	n	xx	XX
		Mean (SD)	xxx.x (xxx.xx)	xxx.x (xxx.xx)
		Median	xxx.x	xxx.x
		Min, Max	XXX, XXX	XXX, XXX
	PD	n	хх	хх
		Mean (SD)	xxx.x (xxx.xx)	xxx.x (xxx.xx)
		Median	xxx.x	xxx.x
		Min, Max	XXX, XXX	XXX, XXX

Baseline=Cycle 1 Day 1
Missing data for intermediate visits are imputed using LOCF.

Source: Listings 16.2.6.3.1, 16.2.6.4

Programming Note: Continue for all visits (Day 1 for each odd-numbered cycle through Cycle 11), including CFB.

Table 14.2.3.3 Overall Response by CFB for WBC A3AR expression ITT Population

	CFB for WBC A3AR		CF102	Placebo
Visit	expression	Overall Response (n, %)	(N=xx)	(N=xx)
Cycle 3 Day 1	< xxx.x (M)	CR	xx (xx.x)	xx (xx.x)
		PR	xx (xx.x)	xx (xx.x)
		SD	xx (xx.x)	xx (xx.x)
		PD	xx (xx.x)	xx (xx.x)
		Total	XX	XX
	>= xxx.x (M)	CR	xx (xx.x)	xx (xx.x)
		PR	xx (xx.x)	xx (xx.x)
		SD	xx (xx.x)	xx (xx.x)
		PD	xx (xx.x)	xx (xx.x)
		Total	XX	XX
Cycle 5 Day 1	< xxx.x (M)	CR	xx (xx.x)	xx (xx.x)
		PR	xx (xx.x)	xx (xx.x)
		SD	xx (xx.x)	xx (xx.x)
		PD	xx (xx.x)	xx (xx.x)
		Total	XX	XX
	>= xxx.x (M)	CR	xx (xx.x)	xx (xx.x)
		PR	xx (xx.x)	xx (xx.x)
		SD	xx (xx.x)	xx (xx.x)
		PD	xx (xx.x)	xx (xx.x)
		Total	XX	XX

CFB=Change from Baseline

Baseline=Cycle 1 Day 1

Percentages are calculated using the number of subjects in the ITT Population for each treatment as the denominator. M=pooled median of CFB for WBC A3AR expression at the specified visit

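### Missing intermediate-visit AFP, A3AR, viral-load and liver-test values are filled by LOCF, can become a change of exactly zero, and are then used as if measured

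*SAP*

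**What the plan says.** - **The rule.** SAP Section 8: "Missing data from intermediate visits for AFP, WBC A3AR, viral load, and laboratory assessments when considered exploratory efficacy variables will be imputed" by LOCF. The same paragraph sets a limit: "Due to the nature of the study, there is no imputation due to discontinuation". It also says that the same laboratory tests are not imputed when shown as safety data.
- **Where it applies.** The LOCF footnote stands under the A3AR tables (14.2.3.1 to 14.2.3.3), the AFP tables (14.2.4.1 to 14.2.4.4), the liver and coagulation tests (14.2.5.x) and viral load (14.2.6).
- **A3AR sampling.** Protocol 9.2.9: "Sampling will be repeated at the beginning of every odd-numbered cycle, unless waived by the Sponsor". SAP Table 1-1 has the same waiver and limits sampling to selected sites.
- **Tests that use the filled values.** For AFP, SAP 7.6.5: "Between-treatment comparisons will be performed by visit using Analysis of Covariance (ANCOVA) with CFB as the dependent variable and Baseline as the covariate". SAP 7.6.6 plans the same for the liver and coagulation tests. For viral load, SAP 7.6.7 plans "ANCOVA with CFB for log-transformed values as the dependent variable and Baseline as the covariate".
- **Response tables.** Table 14.2.3.3 splits subjects at a cut-off defined as "M=pooled median of CFB for WBC A3AR expression at the specified visit" and shows the tumour response in each half. Tables 14.2.4.2 to 14.2.4.4 relate AFP, or its change, to response in the same way.

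Section 8 does not define an intermediate visit, does not say whether baseline may be carried, and does not separate a waived sample from a missed one.

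**The concern.** The A3AR-response relationship and the effect of CF102 on hepatic and viral laboratory parameters are listed secondary objectives, although the SAP presents these variables as exploratory efficacy. A table relating a biomarker to tumour response is informative only if both belong to the same visit. Section 8 does not put tumour response under LOCF, so a current response can be set beside an old biomarker value. In Table 14.2.3.3 a carried baseline adds a zero to the distribution that defines the cut-off. In Table 14.2.4.3 a stale AFP can put a subject in the wrong band.

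In the by-visit ANCOVAs a carried value adds to n without adding information about that visit. It pulls the estimated change toward the earlier value. If visits are missed more often in one arm, the pull differs by arm and creates a difference where none exists.

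**Working it through.** The plan states no missing rate, number of waived samples or biomarker SD, so there is no figure of its own to reproduce.

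**Inputs from the documents.** About 78 subjects randomised 2:1, so 78 × 2/3 = 52 and 78 × 1/3 = 26. A3AR is tabulated on Day 1 of Cycles 3, 5, 7, 9 and 11: five post-baseline visits.

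**Assumed.** Missing rates; independence of missingness from the values; SD 1 at baseline and at the visit; correlation 0.7; a trend common to both arms; the treatment effect; and that baseline may be carried. The ANCOVA figures are for the first post-baseline visit, 2,000 simulated trials per setting unless stated.

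**Step 1: zero change.** If the first post-baseline value is missing and baseline is carried, the change is baseline − baseline = 0.

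**Step 2: how many fills are exact zeros.** Let each of the five A3AR values be missing with probability m.
- If any missing visit is filled, the share of fills equal to zero change is (1 − m⁵) / [5(1 − m)].
- If a visit is intermediate only when a later value exists, visit k is filled with probability m(1 − m^(5−k)) and is a zero fill with probability m^k(1 − m^(5−k)). The share is the ratio of the two sums over k.

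| m | any missing visit filled | later value required |
|---|---|---|
| 0.1 | 22% | 29% |
| 0.2 | 25% | 33% |
| 0.3 | 29% | 39% |
| 0.5 | 39% | 53% |

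**Step 3: shrinkage with equal missingness.** With baseline carried, the expected change given baseline b is (1 − m) × [(0.7 − 1)b + trend + effect × arm], so the ANCOVA estimates (1 − m) × effect. At m = 0.30 and a true effect of -0.50 SD, that is 0.70 × (-0.50) = -0.35. The simulation (trend 0.5 SD) gave -0.35 with LOCF and -0.50 on observed values. The test rejected in 62% of trials with LOCF and 65% on observed values, so the larger n bought no power.

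**Step 4: false difference with unequal missingness.** With no true effect the bias is (placebo missing rate − CF102 missing rate) × trend. For 40% missing on CF102 and 10% on placebo:
- trend 0.5 SD: (0.10 − 0.40) × 0.5 = -0.15 (simulated -0.148)
- trend 1 SD: (0.10 − 0.40) × 1 = -0.30 (simulated -0.301)

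| Missing, CF102 / placebo | Trend | Type I error, LOCF | Type I error, observed |
|---|---|---|---|
| 30% / 30% | 0 | 0.049 | 0.051 |
| 30% / 30% | 0.5 SD | 0.054 | 0.057 |
| 40% / 10% | 0.5 SD | 0.170 | 0.052 |
| 40% / 10% | 1 SD | 0.382 | 0.044 |

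At 20% versus 10% with a 0.5 SD trend, LOCF gave only 0.065 (3,000 runs).

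**Step 5: the response tables.** No arithmetic is needed. A subject with A3AR at baseline and Cycle 5 but not Cycle 3, and a scan read for Cycle 3, enters the Cycle 3 panel of Table 14.2.3.3 with a change of 0 beside a real response.

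**The case against.** The case for leaving the plan alone has real substance.

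- **The limit on LOCF matters.** Filling after dropout, usually its most damaging use, is ruled out. Protocol 4.5.2 cites median survival of generally no more than 2 months after sorafenib in these patients, so much missingness may come from death or discontinuation, which is not filled. This stands.
- **A3AR is not tested between arms.** A reader might infer that waived A3AR samples distort a p-value. They cannot: SAP 7.6.5 and Tables 14.2.3.1 to 14.2.3.3 are descriptive. Sites that never sampled A3AR also have no baseline to carry.
- **Waived is not expressly missing.** That LOCF reaches waived samples follows from the SAP's silence, and a waiver with no later sample may not count as intermediate. This is a reason to write the exemption down.
- **No route to imbalance is shown.** SAP 3.2 keeps the Sponsor blinded, so waivers should not differ by arm, and with equal missingness type I error holds. Shrinkage remains.
- **The variables are exploratory in the SAP.** Correct, and this limits the weight of the point.

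Two further inferences are tempting. One is that viral clearance would be scored as no change because the log of an undetectable result is undefined. The SAP does not say how such results are recorded, and the viral-load listings carry a separate field for whether a sample was taken. The other is that showing the liver tests both with and without imputation is an error. SAP 7.7.2 and Section 8 declare the dual presentation openly.

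**Conclusion.** The point holds as a modest weakness in secondary and exploratory analyses. That unmeasured intermediate values are filled and analysed as observed is stated in the plan. That baseline can be carried, and that waived A3AR samples are included, follows from the absence of any bar.

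The size is unknown. Under the assumptions above, LOCF shrinks a true -0.50 SD difference to -0.35 at 30% missing in both arms. It inflates type I error materially only when missingness differs clearly by arm and the variable drifts over time. The documents do not support saying that filled values are often zero: that is certain at the first post-baseline visit if baseline is carried, and otherwise depends on unstated missing rates. Observed-value analysis is unbiased in these illustrations because missingness was assumed unrelated to the values; if sicker subjects miss samples, neither method is fully protected.

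OS, TTP, PFS and tumour response are outside the LOCF rule, so the primary conclusion does not depend on this.

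**What to change.** In SAP Section 8 and the shell footnotes:

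1. Remove LOCF as the main method for AFP, A3AR, viral load and the exploratory-efficacy laboratory tests.
2. Use only values observed at the visit in Tables 14.2.3.x and 14.2.4.x, including the response cross-tables.
3. Run the planned by-visit ANCOVAs on observed values. Keep LOCF only as a labelled sensitivity analysis, and state there what an intermediate visit is and whether baseline may be carried.
4. State that waived or unscheduled samples are never imputed. This also covers seropositive subjects without measurable baseline viral load, who are in the SAP 7.6.7 analysis set but are not scheduled for later viral-load sampling.

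A different model is not needed; the ANCOVA in Protocol 12.4.2 can stay. Because this SAP version already records decisions taken after unblinding, label the change as made after unblinding and report both versions; SAP Section 9 already sends later changes to the study report.

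The cost is wording and minor programming, with no new data. The downside is a slightly smaller n at some visits.

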#### 9. DIFFERENCES AND CHANGES FROM THE PROTOCOL

The protocol states that disease history includes duration of prior sorafenib therapy, reason(s) for discontinuation of sorafenib, and if applicable, nature of intolerability to sorafenib. The duration is not directly collected, but can be computed from the start and stop dates, as provided for all prior HCC therapies. The reasons(s) for discontinuation, including nature of intolerability, were not collected for prior HCC therapies, including sorafenib.

The protocol states that the listing of "dosing interruptions and dose reductions" will be provided. This listing is not provided, as these data were not specifically recorded, but are available as the "Action Taken" for AEs.

In the protocol, ITT Population is defined as "all subjects in the Safety Population who have any post-Baseline efficacy data, including Liver Chemistry Tests and/or INR on Day 8 of Cycle 1, or death or discontinuation due to disease progression at any time." According to SAP, ITT Population "is defined as all subjects in the Safety Population with any post-Baseline assessment recorded". The difference has no impact, especially since no subjects were excluded from the ITT Population.

Summaries of all safety variables by visit will be presented for visits at which there are at least 4 subjects in either treatment group. AEs, deaths, SAEs, and Discontinuation due to AE are not subject to this constraint. This restriction was not given in the protocol.

Summaries and analyses of efficacy variables by visit will be presented using visits through end of Cycle 11. Analyses of time to event (OS, TTP, and PFS) and Best Overall Response will not be restricted to visits through Cycle 11. This restriction was not given in the protocol.

Analyses of time to event (OS, TTP, and PFS) originally included summary statistics (25th percentile, median, and 75th percentile) from the KM estimate of the survival function and the value of the KM curve at the median duration of therapy. The between-treatment comparisons were performed using the logrank test. After unblinding, it was decided to include the hazard ratio with the corresponding 95% confidence interval from proportional hazards model with no additional covariates and the p-value (Chi-Square). The subgroup analyses of OS (Section 7.6.8) were not presented in the protocol.

After unblinding, it was decided to present incidence of EHS and PVT at Baseline (Section 7.4.2), which are not given in the protocol.

Any changes not presented in this or any subsequent version of the SAP will be described in the clinical study report.

#### 10. APPENDICES

# 10.1 APPENDIX A – CHILD-PUGH CLASSIFICATION OF SEVERITY OF LIVER DISEASE

Child-Pugh classification of severity of liver disease is defined using the degree of ascites, plasma concentrations of bilirubin and albumin, prothrombin time, and the degree of encephalopathy.

Class A (well-compensated disease): total score of 5-6.

Class B (significant functional compromise): total score of 7-9.

Class C (decompensated disease): total score of 10-15.

D	Points Assigned				
Parameter –	1	2	3		
Ascites	Absent	Slight	Moderate		
Bilirubin, mg/dL	<2	2-3	>3		
Albumin, g/dL	>3.5	2.8-3.5	<2.8		
Prothrombin time					
* Seconds over control	1-3	4-6	>6		
* INR	<1.7	1.7-2.3	>2.3		
Encephalopathy	None	Grade 1-2	Grade 3-4		

Parameter	1	2	3
Total bilirubin (µmol/L)	<34	34-50	>50
Albumin (g/L)	>35	28-35	<28

# 10.2 APPENDIX B – DETERMINATION OF OVERALL RESPONSE

Tumor status will be assessed at the Pre-Study Visit, Day 1 of odd-numbered cycles, and at the follow-up visit using Response Evaluation Criteria In Solid Tumors (RECIST), as presented in Appendix A of the protocol. The protocol states that tumor status will be assessed "at baseline and every 8 weeks thereafter (i.e., at the end of even-numbered cycles) by computed tomography (CT) scan or magnetic resonance imaging (MRI)"; however, the "baseline" assessment is performed at the Pre-Study Visit and the assessments of tumor status are recorded on CRF for Day 1 of odd-numbered cycles.

Details regarding the calculation of Overall Response, and related variables, are presented here. The following details are from RECIST v1.1 (Eisenhauer et al. New response evaluation criteria in solid tumours: Revised RECIST guideline (version 1.1). *European J Cancer*. 45(2009): 228-247), the subsequent modification (Santoro et al. Tivantinib for second-line treatment of advanced hepatocellular carcinoma: a randomized, placebo-controlled phase 2 study. *Lancet Oncol*. 2013; 14: 55-63), and the protocol.

At Screening, target lesions are assessed: Up to 5 liver lesions and up to 2 lesions from other organs that can be accurately measured in at least one dimension with longest diameter  $\geq 20$  mm using conventional techniques (CT scan or MRI) or  $\geq 10$  mm with spiral CT scan. The LD for each target lesion should be compared to these minima, and any discrepancies noted for investigation and possible query. Lesions with LD less than these values and lesions from various sites which are "truly non-measurable" (Eisenhauer et al, 2009) are assessed as non-target lesions.

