APPENDIX A: RECIST RESPONSE CRITERIA (V1.1)

NOTE: RECIST v 1.1 as modified by [Santoro \[2013\]](#):

Up to **5 target lesions in the liver and 2 target lesions in other organs** are measured.

RATIONALE: Because HCC often presents as a multifocal disease in the liver and the standard RECIST limitation to a maximum of 2 target lesions in the liver was considered too restrictive for a study with time to progression as the primary endpoint.

available at www.sciencedirect.comjournal homepage: www.ejconline.com

New response evaluation criteria in solid tumours: Revised RECIST guideline (version 1.1)

E.A. Eisenhauer^{a,*}, P. Therasse^b, J. Bogaerts^c, L.H. Schwartz^d, D. Sargent^e, R. Ford^f,
J. Dancey^g, S. Arbuck^h, S. Gwytherⁱ, M. Mooney^g, L. Rubinstein^g, L. Shankar^g, L. Dodd^g,
R. Kaplan^j, D. Lacombe^c, J. Verweij^k

^aNational Cancer Institute of Canada – Clinical Trials Group, [name], Queen's University, Kingston, ON, Canada

^bGlaxoSmithKline Biologicals, Rixensart, Belgium

^cEuropean Organisation for Research and Treatment of Cancer, Data Centre, Brussels, Belgium

^dMemorial Sloan Kettering Cancer Center, New York, NY, USA

^eMayo Clinic, Rochester, MN, USA

^fRadPharm, Princeton, NJ, USA

^gDivision of Cancer Treatment and Diagnosis, National Cancer Institute, Bethesda, MD, USA

^hSchering-Plough, Kenilworth, NJ, USA

ⁱEast Surrey Hospital, Redhill, Surrey, UK

^jNational Cancer Research Network, Leeds, UK

^kErasmus University Medical Center, Rotterdam, The Netherlands

ARTICLE INFO

Article history:

Received 17 October 2008

Accepted 29 October 2008

Keywords:

Response criteria

Solid tumours

Guidelines

ABSTRACT

Background: Assessment of the change in tumour burden is an important feature of the clinical evaluation of cancer therapeutics: both tumour shrinkage (objective response) and disease progression are useful endpoints in clinical trials. Since RECIST was published in 2000, many investigators, cooperative groups, industry and government authorities have adopted these criteria in the assessment of treatment outcomes. However, a number of questions and issues have arisen which have led to the development of a revised RECIST guideline (version 1.1). Evidence for changes, summarised in separate papers in this special issue, has come from assessment of a large data warehouse (>6500 patients), simulation studies and literature reviews.

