3.2.2. Method of assessment

The same method of assessment and the same technique should be used to characterise each identified and reported lesion at baseline and during follow-up. Imaging based evaluation should always be done rather than clinical examination unless the lesion(s) being followed cannot be imaged but are assessable by clinical exam.

Clinical lesions: Clinical lesions will only be considered measurable when they are superficial and ≥ 10 mm diameter as assessed using calipers (e.g. skin nodules). For the case of skin lesions, documentation by colour photography including a ruler to estimate the size of the lesion is suggested. As noted above, when lesions can be evaluated by both clinical exam and imaging, imaging evaluation should be undertaken since it is more objective and may also be reviewed at the end of the study.

Chest X-ray: Chest CT is preferred over chest X-ray, particularly when progression is an important endpoint, since CT is more sensitive than X-ray, particularly in identifying new lesions. However, lesions on chest X-ray may be considered measurable if they are clearly defined and surrounded by aerated lung. See [Appendix II](#) for more details.

CT, MRI: CT is the best currently available and reproducible method to measure lesions selected for response assessment. This guideline has defined measurability of lesions on CT scan based on the assumption that CT slice thickness is 5 mm or less. As is described in [Appendix II](#), when CT scans have slice thickness greater than 5 mm, the minimum size for a measurable lesion should be twice the slice thickness. MRI is also acceptable in certain situations (e.g. for body scans). More details concerning the use of both CT and MRI for assessment of objective tumour response evaluation are provided in [Appendix II](#).

Ultrasound: Ultrasound is not useful in assessment of lesion size and should not be used as a method of measurement. Ultrasound examinations cannot be reproduced in their entirety for independent review at a later date and, because they are operator dependent, it cannot be guaranteed that the same technique and measurements will be taken from one assessment to the next (described in greater detail in [Appendix II](#)). If new lesions are identified by ultrasound in the course of the study, confirmation by CT or MRI is advised. If there is concern about radiation exposure at CT, MRI may be used instead of CT in selected instances.

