Appendix I. Summary of major changes RECIST 1.0 to RECIST 1.1

	RECIST 1.0	RECIST 1.1	Rationale	Reference in special issue (if applicable)
Minimum size measurable lesions	CT: 10 mm spiral 20 mm non-spiral	CT 10 mm; delete reference to spiral scan	Most scans used have 5 mm or less slice thickness Clearer to give instruction based on slice interval if it is greater than 5 mm Caliper measurement will make this reliable	
	Clinical: 20 mm	Clinical: 10 mm (must be measurable with calipers)		
	Lymph node: not mentioned	CT: ≥15 mm short axis for target ≥10–<15 mm for non-target <10 mm is non-pathological	Since nodes are normal structure need to define pathological enlargement. Short axis is most sensitive	Schwartz et al. ¹⁵
Special considerations on lesion measurability	–	Notes included on bone lesions, cystic lesions	Clarify frequently asked questions	
Overall tumour burden	10 lesions (5 per organ)	5 lesions (2 per organ)	Data warehouse analysis shows no loss of information if lesion number reduced from 10 to 5. A maximum of 2 lesions per organ yields sufficient representation per disease site	Bogaerts et al. ¹⁰
Response criteria target disease	CR lymph node not mentioned	CR lymph nodes must be <10 mm short axis	In keeping with normal size of nodes	Schwartz et al. ¹⁵
	PD 20% increase over smallest sum on study or new lesions	PD 20% increase over smallest sum on study (including baseline if that is smallest) and at least 5 mm increase or new lesions	Clarification that if baseline measurement is smaller than any on study measurement, it is reference against which PD is assessed 5 mm absolute increase to guard against over calling PD when total sum is very small and 20% increase is within measurement error	
Response criteria non-target disease	'unequivocal progression' considered as PD	More detailed description of 'unequivocal progression' to indicate that it should not normally trump target disease status. It must be representative of overall disease status change, not a single lesion increase	Confusion with RECIST 1.0 where some were considering PD if 'increase' in any non-target lesion, even when target disease is stable or responding	
New lesions	–	New section on New lesions	To provide guidance on when a lesion is considered new (and thus PD)	

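### SAP Appendix B sets target-lesion size minima that conflict with protocol Appendix A, and outside complete response it shows no short-axis rule for lymph nodes

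*SAP*

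**What the plan says.** **Size of target lesions.** SAP 10.2 (Appendix B) applies RECIST as given in protocol Appendix A. It names RECIST v1.1, the modification from a published second-line HCC trial, and the protocol as its sources. It then sets a minimum longest diameter (LD) of 20 "mm using conventional techniques (CT scan or MRI) or" 10 mm with spiral CT. The next instruction is: "The LD for each target lesion should be compared to these minima, and any discrepancies noted for investigation and possible query". The sentence beginning "Lesions with LD less than these values and lesions from various sites which are" truly non-measurable ends by saying that these "are assessed as non-target lesions".

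Protocol Appendix A differs. In its summary of changes between RECIST versions, the 1.0 column reads "CT: 10 mm spiral 20 mm non-spiral" and the 1.1 column reads "CT 10 mm; delete reference to spiral scan". Its section 3.1.1 sets 10 mm by CT at slices up to 5 mm. For thicker slices, section 3.2.2 says "the minimum size for a measurable lesion should be twice the slice thickness". Its frequently asked questions give MRI the same minimum, provided any inter-slice gap is considered. The protocol's note on the modification allows up to "5 target lesions in the liver and 2 target lesions in other organs" and changes no size.

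**Lymph nodes.** The Target Lesions part of SAP Appendix B records the LD of every target and sums the LDs. It derives target response from Listing 16.2.6.1.2, whose column is the sum of longest diameters. The short axis appears in the text available only in the complete response (CR) definitions for target and non-target lesions. Protocol Appendix A (3.1.1, 4.2, 4.3.2) requires a short axis of at least 15 mm for a nodal target, and requires the short axis in the sum used for PR, SD and PD.

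SAP section 9, which lists differences from the protocol, mentions neither point.

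**The concern.** The SAP states rules that contradict the standard it cites. Overall Response is built from these rules, and TTP, PFS, ORR, DCR and best overall response are built from Overall Response.

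The size rule decides whether a lesion is measured at all. A subject left with no target lesion moves to the SAP's table for non-measurable disease. There the middle category is non-CR/non-PD rather than SD, and DCR counts only CR, PR and SD.

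The nodal rule decides which number enters the sum. A node's long and short axes can change by different amounts, so a PR or PD can be missed or wrongly called. The site-code list for target lesions includes lymph nodes (code 10), and the shell of Table 14.1.4.2 has a row for them. Nodal targets are therefore foreseen, although nothing shows that any exist. A note in the listing shells says no case had all target lesions disappear. The CR rows, the only visible place with a nodal rule, therefore do little work, and target response rests mainly on the sum.

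**Working it through.** The plan gives no figure on this point, so there is none to reproduce. The check compares the two rule sets.

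**1. Size minima for non-nodal lesions.** Appendix A minimum = 10 mm if the slice is ≤5 mm, otherwise 2 × slice (MRI without gaps). SAP minimum = 20 mm for conventional CT or MRI and 10 mm for spiral CT.

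| Slice (mm) | Appendix A minimum (mm) | SAP conventional/MRI too high by (mm) | SAP spiral too low by (mm) |
|---|---|---|---|
| 5 | 10 | 20 − 10 = 10 | 0 |
| 6 | 2×6 = 12 | 20 − 12 = 8 | 12 − 10 = 2 |
| 7 | 2×7 = 14 | 20 − 14 = 6 | 14 − 10 = 4 |
| 8 | 2×8 = 16 | 20 − 16 = 4 | 16 − 10 = 6 |
| 10 | 2×10 = 20 | 0 | 20 − 10 = 10 |

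A 15 mm lesion on conventional CT at 5 mm slices is measurable under Appendix A and non-target under the SAP. A 12 mm lesion on spiral CT at 8 mm slices is the reverse.

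**2. Choosing nodal targets** (conventional CT, slices ≤5 mm). A 22×12 mm node passes the SAP (22 ≥ 20) but fails Appendix A (short axis 12 < 15). An 18×16 mm node fails the SAP (18 < 20) but qualifies under Appendix A (16 ≥ 15).

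**3. The sum.** Assumed baseline: a 40 mm liver lesion and a 30×20 mm node. The Appendix A sum is 40 + 20 = 60 mm; the LD sum is 40 + 30 = 70 mm. PD needs a rise of at least 20% and 5 mm over the smallest sum, here the baseline. PR needs a fall of at least 30% from baseline.

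With the liver lesion unchanged, PD requires:
- Appendix A: short axis ≥ 1.2×60 − 40 = 32 mm
- LD sum: long axis ≥ 1.2×70 − 40 = 44 mm

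| Follow-up | Appendix A sum | LD sum |
|---|---|---|
| Liver 40, node 38×34 | 60→74, +23.3%: PD | 70→78, +11.4%: not PD |
| Liver 40, node 46×26 | 60→66, +10.0%: not PD | 70→86, +22.9%: PD |
| Liver 30, node 24×11 | 60→41, −31.7%: PR | 70→54, −22.9%: not PR |
| Liver 30, node 18×16 | 60→46, −23.3%: not PR | 70→48, −31.4%: PR |

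Both categories can change in both directions. These sizes were chosen to show direction, not likelihood.

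**4. Weight of one subject.** 78 at 2:1 gives 52 and 26. One reclassified subject moves a response rate by 1/52 = 1.9 percentage points on CF102 or 1/26 = 3.8 on placebo.

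**The case against.** The strongest reply is that no effect on any analysis has been shown.

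- The SAP cites the right standard, and the protocol sends sites to its Appendix A when they choose targets at screening. SAP Version 7.0 contains decisions taken after unblinding, so at least this version cannot have guided that choice.
- For a recorded target below the minimum, the only stated action is a note and a possible query. Nothing removes it from the sum, and per-protocol exclusion concerns the number of target lesions, not their size.
- On nodes, the response table after the PR row, the shells of the tumor response listings and the CRF were not available for this review. The PR row refers to diameters without the word longest, and LD may be only a label over short axes that sites entered. The site-code list is generic, so a lymph-node code is weak evidence.
- The node examples were picked to cross thresholds, and 1/52 and 1/26 only restate arm size.
- Counting small recorded targets cannot find lesions that sites placed among the non-targets, because those need no measurement and Listing 16.2.6.2 has no size column.

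Most of this stands as a limit on size and certainty. The last point also limits what a check can recover. None of it removes the contradiction: the text sets minima its cited sources do not support and defines the sum by longest diameter for every target. The unavailable pages do not alter that sum, which the Target Lesions text and Listing 16.2.6.1.2 both define.

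**Conclusion.** The concern holds, and the text should be corrected. The size minima are wrong against the SAP's own reference: too strict for 10 to <20 mm lesions on conventional CT or MRI at thin slices, and too loose for spiral CT at slices above 5 mm. The nodal part is wrong as written, because the longest-diameter sum has no visible exception for nodes.

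Overall survival, the primary endpoint, is unaffected. What is exposed is TTP, PFS, ORR, DCR and best overall response. The size of any effect cannot be estimated, because the documents give no imaging modality, slice thickness, lesion sizes or count of nodal targets. An effect of the nodal rule requires that nodal targets exist and that long axes were recorded. An effect of the size rule on recorded targets depends on how the queries are resolved. If sites entered short axes, the nodal part reduces to wording. Confidence is medium for these reasons.

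**What to change.** **Text.** In SAP Appendix B, replace the minima with those of protocol Appendix A:
- LD ≥10 mm by CT at slices ≤5 mm, otherwise twice the slice thickness
- the same for MRI without an inter-slice gap, with any gap taken into account
- short axis ≥15 mm for nodes

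Define the sum as longest diameter for non-nodal targets plus short axis for nodal targets.

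**Checks.**
1. Read the number of code-10 targets by arm from Table 14.1.4.2. If there are any, confirm which axis was recorded, then relabel Listings 16.2.6.1.1 and 16.2.6.1.2 to match.
2. From Listing 16.2.6.1.1, count 10–19 mm targets imaged by conventional CT or MRI (method codes C and M). Resolve size queries against the Appendix A minima, so that qualifying lesions stay targets.
3. Do any re-derivation blind to treatment arm, because this SAP already contains post-unblinding changes.
4. Disclose the change in SAP section 9 or, as that section allows, in the clinical study report. Report as limitations any node whose short axis cannot be recovered, and that small lesions placed among the non-targets cannot be identified from the listings.

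**Cost.** Wording, shell labels and counts from planned outputs. Listing 16.2.6.1.1 has no column for slice thickness or gap, so a site query is needed for each 10–19 mm conventional CT or MRI target and each spiral CT target below 20 mm. Nodal queries arise only if code-10 targets exist.
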